7.3 Breaking the Blind

At the initiation of the study, the Investigator will be instructed on the method for breaking the blind during the Core Phase. The blind is not to be broken during the study unless considered necessary by the Investigator for emergency situations and/or for reasons of subject safety. Unblinding at the clinical site for any other reason will be considered a major protocol deviation. The Investigator should contact the Medical Monitor before breaking the blind, if possible. The reason for breaking the blind should be fully documented.

7.4 Drug Supplies

7.4.1 Labels and Packaging

7.4.1.1 Avatrombopag Film-Coated Oral Tablets or Matching Placebo

A sufficient supply of avatrombopag or placebo oral tablets will be provided to the clinical site. Avatrombopag will be provided as film-coated tablets, with each tablet containing avatrombopag maleate (equivalent to 20 mg of avatrombopag) and excipients. Matching placebo tablets will also be provided for the Core Phase.

During the Extension Phase, avatrombopag film-coated oral tablets will be packaged in open-label packages.

The clinical site will dispense the number of tablets required for dosing each subject for a 30 day period (e.g., a monthly supply of thirty 20 mg tablets for a 20 mg daily dose).

7.4.1.2 Avatrombopag Powder for Oral Suspension in a Capsule or Matching Placebo

A sufficient supply of avatrombopag or placebo capsules, which can be opened to sprinkle the contents into an appropriate vehicle, will be provided to the clinical site. Each avatrombopag capsule

will contain avatrombopag maleate (equivalent to 10 mg avatrombopag) and excipients. Matching placebo capsules, containing the same excipients as the active capsules, will also be provided for the Core Phase.

During the Extension Phase, avatrombopag capsules will be packaged in open-label packages.

The clinical site will dispense the number of capsules required for dosing each subject for a 30 day period (e.g., a monthly supply of sixty 10 mg capsules for a 20 mg daily dose).

7.5 Avatrombopag Administration

Subjects will receive avatrombopag, or matching placebo, in the Core Phase, as either the film-coated oral tablet or the powder for oral suspension in a capsule that can be opened to sprinkle the powder for oral suspension into an appropriate vehicle. No partial dosing from the capsule is allowed; the entire contents of the capsule should be used.

During the Core Phase, subjects in Cohort 1 (aged \geq 12 to <18 years) and Cohort 2 (aged \geq 6 to <12 years) will receive the oral tablet and subjects in Cohort 3 (aged \geq 1 to <6 years) will receive the powder for suspension in a capsule. The formulation received should be recorded in the eCRF.

Study drug will be taken by mouth, with food, and the first dose will be administered by the study team while the subject is at the site for Day 1/Visit 2 during the Core Phase. Palatability and acceptability of the powder for oral suspension will be assessed after the first dose of study drug during the Core Phase in subjects in Cohort 3 (Table 7; Appendix B).

Instructions for administration of the oral tablet and the powder for oral suspension in a capsule will be provided in a separate document.

The date and time of administration of each dose of study drug (administered at home or in-clinic) should be recorded by the subject, or the subject's LAR, on the provided Dosing Diary.

7.6 Receipt of Supplies

Upon receipt of the study drug, the pharmacist, or designee, will visually inspect the shipment and verify drug information, quantity, and condition of the study drug received.

7.7 Study Drug Storage Conditions

Study drug should be stored in a secure location at a controlled room temperature of 20°C to 25°C (68°F to 77°F) and protected from light and moisture. The storage location must be a locked room with limited access, available to appropriate study personnel only.

7.8 Treatment Compliance

The first dose of study drug will be taken while the subject is at the site during Day 1/Visit 2. During this visit, subjects and/or their caregiver, as applicable, will be provided with instructions on appropriate at-home study drug administration.

Regardless of the subject's current treatment regimen (once daily, three times a week, etc.) Visit 4 and Visit 12 must fall on a day the subject is scheduled to take their dose of study drug. During Visit 4 (Week 2) and Visit 12 (Week 10) subjects will receive the dose of study drug while at the site after

the pre-dose PK sample has been collected (Section 9.6). Administration date and time, including the vehicle and the volume of the vehicle used with the powder for oral suspension, will be documented in the eCRF.

When taking study drug at home, subjects and/or the subject's LAR should record the date and time of each dose of study drug, as well as the vehicle and volume of vehicle used for ingestion of the powder for oral suspension, as applicable, in the provided Dosing Diary.

Study personnel should review the Dosing Diary at applicable visits (Appendix A) to ensure accuracy of the entries on the diary.

7.9 Study Drug Accountability

The Sponsor will provide the Investigators with sufficient amounts of study drug for this study. It is the responsibility of the Investigator to ensure that a current record of inventory/drug accountability is maintained. Inventory records must be readily available for inspection by the study Clinical Research Associate (CRA), the Sponsor (or designee), or regulatory authorities. The study team should perform a count of unused study drug returned from the subject at the frequency defined in the Core Phase and the Extension Phase Schedule of Events in Table 7 and Table 8.

7.10 Study Drug Handling and Returns

Upon completion or termination of the study, and upon written authorization from the Sponsor, or its designee, unused and/or partially used study drug should be returned or destroyed at the investigational site. It is the Investigator's responsibility to ensure that the Sponsor or its designee has provided written authorization for proper disposal of study drug, and that appropriate records of the disposal are documented and maintained. No unused study drug may be disposed of until fully accounted for by the Sponsor, or designee.

8 PRIOR AND CONCOMITANT MEDICATIONS AND/OR PROCEDURES

8.1 Documentation of Prior and Concomitant Medications

All concomitant medications (including concurrent therapies and concurrent procedures) will be documented from the time of informed consent/assent through study discharge in the source documents and the eCRF. Dose, frequency, indication for administration, and dates of medication administration will be captured for all medications taken within 90 days of Screening.

8.2 Contraception Requirements

For this study, a woman is considered of childbearing potential, i.e. fertile, following menarche unless permanently sterile. Permanent sterilization methods include hysterectomy, bilateral salpingectomy and bilateral oophorectomy.

- Females of childbearing potential who are sexually active must agree to use highly effective methods of birth control (i.e., oral or injectable contraceptive in combination with a second method, contraceptive implant, indwelling intrauterine device (IUD), or a vasectomized partner) while participating in the study and for 30 days after the last dose of study drug.
- Males who are sexually active must agree that their female partner has had a bilateral tubular occlusion or agree to use a male condom plus spermicide combined with female diaphragm plus spermicide while participating in the study and for 30 days after the last dose of study drug.
- Sexual abstinence is acceptable as an effective method of birth control only as true abstinence: when this is in line with the preferred and usual lifestyle of the subject. Periodic abstinence (e.g., calendar, ovulation, symptothermal, post-ovulation methods) and withdrawal are not acceptable methods of contraception.

8.3 Permitted ITP Concomitant Background Medications

The following medications are permitted as concomitant background medications as long as they are taken at a stable dose for the specified amount of time prior to Day 1/Visit 2. The dose/frequency as well as any dose changes must be recorded in the eCRF.

- Corticosteroids or azathioprine/6-mercaptopurine taken at a stable dose for at least 30 days before Day 1/Visit 2.
- MMF, CsA, sirolimus, or danazol taken at a stable dose for at least 90 days before Day 1/Visit 2.

8.4 Concomitant ITP Medication Dose Reduction

Any permitted concomitant ITP medications taken at Day 1/Visit 2 by the subject during the Core Phase may be down titrated in order to maintain the subject's platelet count between $\geq 50 \times 10^9/L$ and $\leq 150 \times 10^9/L$. Downward concomitant ITP medication titration will be at the discretion of the Investigator, all dose changes must be recorded in the eCRF.

8.5 Prohibited Medications and/or Procedures

The following medications and/or procedures are prohibited:

- Immunoglobulins (IVIg and anti-D) are prohibited during the study unless needed as a rescue therapy (Section 8.6). Immunoglobulins must have been completed at least 14 days prior to Day 1/Visit 2.
- Platelet transfusion, or receipt of blood products containing platelets, within 7 days of Day 1/Visit 2 and during the study unless needed as a rescue therapy (Section 8.6). Packed RBCs are permitted.
- Cyclophosphamide and vinca alkaloid regimens must have been completed at least 30 days prior to Day 1/Visit 2.
- Splenectomy and rituximab must have been completed at least 90 days prior to Day 1/Visit 2.
- Use of other TPO-RAs (e.g., eltrombopag or romiplostim) or recombinant human TPO within 28 days prior to Day 1/Visit 2 and during the study.
- Use of vitamin K antagonists, antifibrinolytic agents, recombinant activated factor VII, heparin, factor Xa inhibitors, direct thrombin inhibitors, desmopressin, or chronic antiplatelet therapy (>30 days) during the study.
- Previous therapy with moderate or strong dual inducers or moderate or strong dual inhibitors of CYP2C9 and CYP3A4 must have been completed within 7 days of Day 1/Visit 2 (Appendix D).
- Enrollment in another clinical study with any investigational drug or device within 30 days of Screening or during the study; however, participation in observational studies within the previous 30 days is permitted.

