Second-line treatment options in children include rituximab (an immune suppressing agent) and the TPO receptor agonists (TPO-RAs) eltrombopag (PROMACTA®/REVOLADE®) and romiplostim (NPLATE®). Rituximab has effects on the immune system that may last longer than the disease course and can also be associated with infusion-related side effects and persistent hypogammaglobulinemia. Eltrombopag must be taken 2 hours before or 4 hours after any antacids, dairy products, or mineral supplements containing polyvalent cations and must also be taken on an empty stomach, 1 hour prior to eating or 2 hours after eating, which may be challenging for children. Romiplostim requires weekly subcutaneous injections which are typically performed by the patient's healthcare provider. Finally, splenectomy is discouraged in children due to the high rates of spontaneous remission in this population as well as the short and long-term risks of asplenia (PROMACTA® United States Prescribing Information [USPI]/REVOLADE® Summary of Product Characteristics [SmPC]; NPLATE® USPI; NPLATE® SmPC; Neunert, 2019; Provan, 2019).

There remains an important unmet medical need for new treatment options for pediatric patients with ITP, given the difficult administration requirements and the variable, transient response, frequent relapse, and associated toxicities of the available treatments.

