8.6 Rescue Therapies

Subjects may receive rescue therapy at the discretion of the Investigator if there is an urgent need to increase platelet count, such as in the case of life-threatening thrombocytopenia, in the opinion of the Investigator, clinical signs and symptoms suggesting a potential bleed (e.g., wet purpura) or a major bleed. All rescue medications, including dose and frequency, must be recorded on the eCRF.

Rescue therapy may include:

- The addition of any *new* ITP medication or medication to treat thrombocytopenia, such as:
 - Corticosteroids
 - o IVIg
 - o Anti-D
 - Platelet transfusion
- Any *increase in the Day 1/Visit 2 dose* of a concomitant ITP medication.
- TPO-RAs are not allowed as rescue therapy.

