7.3.5 Prior and Concomitant Medications

All medications will be coded using Anatomical Therapeutic Chemical (ATC) classification based on World Health Organization (WHO) Drug Dictionary (March 2020, B3 or higher). The coding version may be updated prior to database lock if a newer version is available.

Prior medications are medications taken and stopped prior to first dose of study drug.

Concomitant medications during the Core Phase are medications being taken on or after the first dose of study drug in the randomized control period and prior to the first dose of the study drug in the Open Label Extension period.

Medications that start before the first dose of study drug in the randomized control period and continue into the randomized control period will be considered as concomitant medications for the Core Phase.

Concomitant medications for the Open Label Extension period are those which begin prior to the open label extension period and continue into the Open Label Extension period or those which start on or after the first day of study treatment in the Open Label Extension period.

Medications that begin in the Core Phase and have missing end dates are assumed to be

concomitant medications in both Core Phase and Open Label Extension Phase.

The number and percentage of subjects who have taken prior or concomitant medications will be summarized by ATC Level 2 Category and Preferred Name. A subject will be counted only once for medications taken more than once.

Rescue therapy may include:

- The addition of any new ITP medication or medication to treat thrombocytopenia, such as:
 - Corticosteroids ATC level 2: CORTICOSTEROIDS FOR SYSTEMIC USE
 - IVIg ATC level 2: IMMUNE SERA AND IMMUNOGLOBULINS
 - Anti-D Preferred Term: Anti-D (rh) immunoglobulin
 - Platelet transfusion Concomitant Procedure
- Any increase in the Day 1/Visit 2 dose of a concomitant ITP medication

TPO-RAs are not allowed as rescue therapy.

The following summary will be provided:

- Concomitant medications by study phase (Core Phase and Open Label Extension Phase)
- Concomitant Medications taken as rescue for a bleeding event by study phase (Core Phase and Open Label Extension Phase)
- Rescue Therapy used by study phase (Core Phase and Open Label Extension Phase)

Prior and concomitant medications will be listed for the Full Analysis Set.

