7.4 Efficacy Analysis

Unless otherwise stated, all primary and secondary efficacy endpoints defined in Section 3.2.1 will be analyzed for the FAS and PPS.

For the efficacy evaluation of the platelet count responses, platelet counts assessed by local labs will be used. Platelet counts collected via the central lab will be used in the safety assessments of

clinical laboratory tests.

The methods used for efficacy analysis for the Core Phase are summarized in Error! Reference source not found.3. All Cochran-Mantel-Haenzel (CMH) tests at alpha=0.05 within each age cohort will be performed adjusting for baseline platelet count category ($\leq 15 \times 10^9 / L \text{ vs} > 15 \times 10^9 / L$). For the CMH test in the overall group, the test will be performed adjusting for age cohort and baseline platelet count category. Fisher's exact test will be used if the number of durable platelet responders is spare in the strata (less than 3 in a specific subgroup). Durable platelet response with 2-sided 95% exact binomial (Clopper-Pearson) confidence interval (CI) will be provided. The difference in response rate (avatrombopag – placebo) with 2-sided 95% CI (Wald) will also be provided.

Subjects without sufficient data for the determination of response status (i.e., responder versus non-responder) will be treated as non-responders in the analysis.

For the primary efficacy endpoint determination, a subject must have remained in the Core phase through at least Week 10 (to have at least 6 weeks of platelet count data starting from week 5 to either week 12 if the subject completes the core phase or the last week if the subject prematurely terminates the core phase). If a subject terminates the Core phase prior to Week 10, they would be considered a non-responder for the primary efficacy endpoint.

Endpoint	Analysis Method
Primary Efficacy Endpoint	
Durable platelet response defined as proportion of subjects achieving at least 6 out of 8 weekly platelet counts $\geq 50 \times 10^9 / L$ during the last 8 weeks of the 12 week treatment period in the Core Phase in the absence of rescue medication. In the case of rescue medication being used, platelet count assessments from the start date of rescue medication up until 4 weeks after the end date of rescue medication will be excluded from analysis.	CMH test

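### Protocol 8.5 and 8.6 conflict on whether rituximab may be given during the Core Phase, and the SAP's single 4-week exclusion could let counts after it be scored as durable response

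*Protocol*

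**What the plan says.** Protocol 8.5 opens with "The following medications and/or procedures are prohibited". Its bullets then differ in wording. Those on platelet transfusion, TPO-receptor agonists and anticoagulant-type drugs extend the bar to the study itself. So does the immunoglobulin bullet, which adds a rescue exception: "Immunoglobulins (IVIg and anti-D) are prohibited during the study unless needed as a rescue therapy (Section 8.6"). Platelet transfusion has the same exception. Two bullets state only a washout before Day 1: "Splenectomy and rituximab must have been completed at least 90 days prior to Day 1/Visit 2" and "Cyclophosphamide and vinca alkaloid regimens must have been completed at least 30 days prior to Day 1/Visit 2".

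Protocol 8.6 and SAP 7.3.5 define rescue openly: "The addition of any new ITP medication or medication to treat thrombocytopenia, such as" corticosteroids, IVIg, anti-D and platelet transfusion. The one named exclusion is "TPO-RAs are not allowed as rescue therapy".

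Protocol 6.3.2 lists needing a prohibited concomitant medication among the reasons for which a subject may be terminated early.

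For the primary endpoint, SAP 7.4 Table 3 says that "platelet count assessments from the start date of rescue medication up until 4 weeks after the end date of rescue medication will be excluded from" the analysis. No agent is treated differently. The primary analysis uses the full analysis set. SAP 6.6 mentions prohibited medication only as an example of a per-protocol exclusion.

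Protocol 1.2 says "Rituximab has effects on the immune system that may last longer than the disease course".

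**The concern.** An investigator facing an urgent bleed could read 8.5 as forbidding rituximab, or 8.6 as covering it under any new ITP medication. The documents should give one answer.

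The statistical issue follows if it is used. The primary endpoint is meant to measure durable response without rescue. A 28-day exclusion may suit short-acting rescue. The protocol treats rituximab as needing 90 days to clear before entry, which is longer than the whole 84-day Core Phase. Under the SAP rule, a child given rituximab early could re-enter the count and be scored a durable responder to study drug or to placebo. The placebo arm has only 18 children, so one misclassified child there has some weight.

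**Working it through.** **Inputs.** Weekly visits fall on Day 7w + 1 for Week w (Protocol Table 7). The primary window is Weeks 5 to 12, Days 36 to 85, and at least 6 of 8 counts must reach 50×10⁹/L. The exclusion lasts to 28 days after rescue ends (SAP Table 3). Entry washouts are 90 days for rituximab and splenectomy, and 30 days for cyclophosphamide and vinca alkaloids (Protocol 8.5). Planning assumptions are 54 versus 18 children, 41.3% versus 3.4%, two-sided α = 0.05, Fisher's exact test (Protocol 11.3).

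**The plan's own figure.** Exact enumeration of the two-sided Fisher test gives 94.5% power, consistent with the stated minimum of 90%.

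**Primary endpoint.** Let E be the day rescue ends. A count is usable if 7w + 1 > E + 28.

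| Rescue ends | Usable counts, Weeks 5–12 |
|---|---|
| Day 1–7 | 8 |
| Day 8–14 | 7 |
| Day 15–21 | 6 |
| Day 22–28 | 5 |

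Six counts require Week 7 (Day 50) to be usable, so E + 28 < 50, which gives E ≤ 21. The ±1-day visit window moves this to Day 20–22. If one assumes, for illustration only, four weekly doses from Day 1, the course ends on Day 22, leaves five counts and misses the primary route. Only shorter courses reach it.

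**Alternative primary endpoint.** Two consecutive counts are needed, the last usable pair being Days 78 and 85. If the same 28-day rule is applied (Table 3 states it only in the primary row), E + 28 < 78, so E ≤ 49.

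**Against the protocol's own washouts.**
- Rituximab: 1 + 90 = 91 > 85. Even a Day 1 dose would leave no usable Core count if 90 days were applied.
- Cyclophosphamide and vinca alkaloids: E + 30 < 50 gives E ≤ 19 instead of 21. The difference is 30 − 28 = 2 days.

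**What one misclassified child could do (hypothetical).** The result depends on how the false placebo responder is modelled:

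| Model | Power |
|---|---|
| None | 94.5% |
| One of the 18 fixed as a responder, the other 17 at 3.4% | 82.1% |
| One added to the count from 18 at 3.4% | 81.2% |
| Placebo rate raised by 1/18 | 76.5% |
| One false responder on avatrombopag instead (rate raised by 1/54) | 96.2% |

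The smallest significant avatrombopag count is 12 of 54 with no placebo responder and 17 of 54 with one. Near the planned rates, 22/54 versus 1/18 gives p = 0.007, and 22/54 versus 2/18 gives p = 0.023.

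**The case against.** A reader might infer that 8.6 permits rituximab during the Core Phase. The documents do not support that. The lead-in to 8.5 prohibits everything in its list, and only immunoglobulins and platelet transfusion have a rescue exception. Prohibition is the more natural reading. Barring children who require rituximab or splenectomy from the Extension Phase (6.2.2) is consistent with it. What remains is that the rituximab bullet lacks the on-study wording of its neighbours and that 8.6 names a single exclusion.

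Termination under 6.3.2 is a partial safeguard. A child who leaves the Core Phase before Week 10 is a non-responder under SAP 7.4. But termination there is discretionary, so the scoring route is narrowed and not closed.

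A reader might also extend the scoring problem to every agent in 8.5 worded only as a washout. That fails for cyclophosphamide and vinca alkaloids: the gap is 2 days, and the protocol describes a lasting effect for rituximab only. Splenectomy is not a medication, so the medication wording in 8.6 does not admit it as rescue.

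Finally, the 90-day washout is an entry criterion, and nothing makes it a rule for admitting on-study counts. That is correct. It serves here only as the protocol's own indication that 28 days may be short for this drug.

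**Conclusion.** The point holds as a minor one. Protocol 8.5 and 8.6 do not agree clearly on rituximab, or on the other agents worded only as a washout, and must be reconciled together with 6.3.2. Which answer is right is a clinical matter not judged here.

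On the analysis side, the stated rule would allow counts after rituximab ending by about Day 21 to be scored as durable response in the full analysis set. The corresponding limit for the alternative endpoint is Day 49 if the same exclusion is applied.

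This rests on nominal visit days, on rituximab being used despite 8.5, and on the child staying in the Core Phase to at least Week 10. The documents give no frequency, and such use is expected to be rare. A false placebo responder works against avatrombopag and a false avatrombopag responder works for it, so the direction of bias is not fixed. The power losses shown are hypothetical and should not be read as an error in the sample size; the stated power is reproduced.

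**What to change.** 1. **Protocol:** reconcile 8.5, 8.6 and 6.3.2 so that they give one answer on whether rituximab, and the other agents in 8.5 worded only as a washout, may be given during the Core Phase.
2. **SAP Table 3, before unblinding:** add one line covering all platelet-response endpoints. After any on-study rituximab, or splenectomy should it occur, later Core counts are not counted as response. The child is a non-responder unless response was already established before that treatment.

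The line should name these two treatments. A general trigger based on washouts longer than 28 days would also catch corticosteroids and other agents with a more-than-30-day washout in inclusion criteria 5 and 6, and corticosteroids are the first-listed rescue drug. Cyclophosphamide and vinca alkaloids need no separate scoring rule (30 versus 28 days).

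The cost is one protocol clarification and one SAP line. The downside is small: a rare child whose later counts reflect study drug would be scored a non-responder.
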